10.10 Laboratory Assessments

Laboratory results marked as clinically significant will be categorized as, "Abnormal, CS" and results marked as not clinically significant will be categorized as, "Abnormal, NCS". Results within normal range will be marked as "Normal". Not done results will be categorized as, "Not Done".

If repeat assessments are taken within the same scheduled visit/date, then the latest assessment will be considered for analysis. All laboratory parameters will be reported in SI units.

10.11 painDETECT Questionnaire

The PD-Q total scores (range -1 to 38) indicating a neuropathic pain component will be categorized as follows: ≤ 12 = Unlikely, 13-18 = Uncertain, ≥ 19 = Likely

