10.2 Laboratory assessments

10.2.1 Clinical safety testing

Blood and urine samples will be taken at screening, on Days 1, 28, 50, 77 and at the end of study visit. Blood samples will be tested at one nominated laboratory per study site. Urinalysis (dipstick) will be performed at the investigational site.

Details of the volume of blood and type of tubes required for the following tests will be provided in the Study Manual. At the investigator's discretion, sample collection may be repeated if an abnormal result occurs due to technical or other reasons.

The following tests will be performed.

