7.5 Exploratory endpoints

1. *Association between change in mean NPRS from baseline to the end of four weeks treatment and selected subject baseline characteristics, including clinical diagnosis and pre-treatment [REDACTED]*
2. *Change from baseline in [REDACTED] [REDACTED] to the end of 4 weeks treatment, in each treatment period*
3. *Correlation between plasma LAT8881 concentration and the change in mean NPRS from baseline to the end of four weeks treatment in PK subjects*
4. *Change in mean NPRS score from baseline to the last week of each treatment period, after omission of subjects with the 25% most variable first baseline NPRS scores*

8 Statistical Methods

Efficacy endpoints will be summarized in a descriptive manner and analyzed using statistical methods described in section 11.7. The level of significance for statistical tests will be 0.05 and all tests will be two-sided. All p-values will be displayed to four decimal places, with p-values less than 0.0001 presented as '<0.0001' and p-values greater than 0.9999 presented as '>0.9999'. All analyses will be done using SAS [REDACTED]

Safety endpoints will be summarised in a descriptive manner.

Continuous data will be reported using the following descriptive statistics:

1. Number of observations (n)

2. Mean and standard deviation (SD)
3. Minimum (min) and maximum (max)
4. Median

Minimum and maximum values will be reported to the precision of the endpoint reported with maximum of three decimal places; the mean will be presented with one decimal place more and the standard deviation two decimal places more than the precision of the endpoint reported. Categorical data will be presented using frequency (n = number of subjects; m = number of events) and percentage (%).

Listings will be provided for all data recorded in eCRF to study subject profiles. All listings will be sorted by treatment sequence, subject ID, study period and date (if applicable). Unscheduled visit data will only be listed and not included in summaries.

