11.7.2 Laboratory Assessments

11.7.2.1 Continuous Summary

Descriptive summaries of the absolute result and change from baseline in laboratory data will be presented by treatment overall and within each study period, parameter and visit for the safety population. Each laboratory category (haematology, clinical chemistry, liver function tests, coagulation, urinalysis) will be represented in separate tables. Both categorical and continuous results will be presented in the same table for urinalysis.

In DDP: Table 14.3.4.1 to Table 14.3.4.5

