11.7.2.2 Shift Summary

Shift in laboratory result interpretations (Normal, Abnormal Not CS and Abnormal CS) will be summarized by treatment within each study period and overall, parameter and visit. Each category (haematology, clinical chemistry, liver function tests, coagulation) will be represented in separate tables. Percentages will be based on safety population.

In DDP: Table 14.3.4.6 to 14.3.4.9

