11.7.2.3 Listings

All laboratory results will be listed for all subjects by treatment sequence, visit and parameter. Out of range results will be highlighted. Pregnancy results collected on Screening and Day 1 will be listed separately.

In DDP: Listing 16.2.8.1 to 16.2.8.5, Listing 16.2.8.7

Subjects with clinically significant laboratory results and subjects with out of range results will be separately listed by treatment sequence, category, visit and parameter. In DDP: Listing 16.2.8.6

Parameters collected in each laboratory category are listed below.

Category	Parameters
Haematology	Haemoglobin, haematocrit, red blood cell count, white blood cell count with differential (neutrophils, lymphocytes, monocytes, basophils, eosinophils), platelet count, mean corpuscular haemoglobin, mean corpuscular volume, mean corpuscular haemoglobin concentration
Clinical Chemistry	Glucose, sodium, potassium, chloride, bicarbonate, calcium (corrected), creatinine, urea, uric acid, amylase, lipase, triglyceride, HDL-cholesterol, LDL-cholesterol, total cholesterol, total protein, lactate dehydrogenase, creatine kinase, C-reactive protein, albumin, phosphate. HbA1c will be measured in DPN subjects only and only at screening.
Liver Function Tests	Aspartate aminotransferase, alanine aminotransferase, gammaglutamyl transferase, alkaline phosphatase, conjugated bilirubin, total bilirubin
Coagulation	Activated partial thromboplastin time, international normalised ratio
Urinalysis	Specific gravity, pH, glucose, protein, blood, ketones, urobilinogen, bilirubin, nitrite, leukocytes. If urinalysis on dipstick is positive for leukocytes and/or blood/haemoglobin, a microscopic examination including erythrocytes, leucocytes, bacteria, casts, epithelial cells and crystals will be performed.
Pregnancy	Human chorionic gonadotropin levels (hCG) will be measured in blood samples from females of child-bearing potential at screening. Urine hCG will be measured on Day 1.

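### Two SAP rules can keep valid abnormal laboratory values out of the by-treatment laboratory summaries, and no worst post-dose table is planned to recover them

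*SAP*

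**What the plan says.** Four provisions meet here.

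- **Repeats within a visit.** SAP 10.10: "If repeat assessments are taken within the same scheduled visit/date, then the latest assessment will be considered for analysis". No distinction is made between a repeat that replaces a failed sample and one that checks a valid result.
- **What prompts a repeat.** Protocol 10.2.1: "At the investigator's discretion, sample collection may be repeated if an abnormal result occurs due to technical or other reasons".
- **Unscheduled results.** SAP Section 8: "Unscheduled visit data will only be listed and not included in summaries".
- **The tables.** SAP 11.7.2.1: "Descriptive summaries of the absolute result and change from baseline in laboratory data will be presented by treatment overall and within each study period", by parameter and visit. SAP 11.7.2.2: "Shift in laboratory result interpretations (Normal, Abnormal Not CS and Abnormal CS) will be summarized by treatment", also by visit, for haematology, clinical chemistry, liver function and coagulation. Neither section plans a summary of the worst value after dosing.

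Two provisions limit the damage. SAP 11.7.2.3 says "All laboratory results will be listed for all subjects by treatment sequence, visit and parameter. Out of range results will be highlighted", with separate listings of clinically significant and of out-of-range results. Protocol 12.3 requires an abnormal finding to be recorded as an adverse event if it is clinically significant or accompanied by signs or symptoms.

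**The concern.** The protocol names an abnormal result as the occasion for a repeat and gives no corresponding reason to recheck a normal one. Using the latest value therefore acts in one direction: a high value that falls back on recheck becomes normal in the tables, while a value that was normal by chance is left alone. Part of that falling back is ordinary regression to the mean.

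The unscheduled rule opens a different gap. Under the protocol's schedules of assessments, the Day 1 and Day 50 safety samples are pre-dose, so each treatment period has one scheduled on-treatment sample, on Day 28 or Day 77. An abnormality found between those points, and gone by the next scheduled sample, appears in no laboratory table.

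At stake is the comparative description of laboratory safety, which is a named safety endpoint. The most exposed category is abnormal but not clinically significant: such values usually do not become adverse events, so the laboratory tables are the only planned place where they are counted by treatment.

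**Working it through.** **Step 1. What each rule does to an abnormal value.** The documents give no figure to reproduce, so the rules are set against the possible cases.

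| Case | Value in the by-visit tables |
|---|---|
| Abnormal at a scheduled visit, no repeat | The abnormal value |
| Abnormal at a scheduled visit, repeat recorded under the same visit/date | The repeat; the abnormal value is displaced |
| Abnormal at a scheduled visit, repeat taken as an unscheduled visit | The abnormal value; the repeat is left out |
| Abnormality first found at an unscheduled visit | None |

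Rows 2 and 4 lose values; row 3 does not. A blood recheck on a later day could fall in row 2 or row 3, because SAP 10.10 pairs visit with date and does not say which governs.

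**Step 2. Size of the row 2 loss (illustration).** The documents give no test-retest correlation and no recheck frequency, so these are assumptions: original and repeat are bivariate normal with correlation r and a stable true value; the upper limit lies at the 97.5th percentile (z = 1.96); every flagged value is rechecked within the visit. Then

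share lost = 1 − P(both > 1.96) / P(first > 1.96), with P(first > 1.96) = 0.0250.

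| r | P(both > 1.96) | P(repeat high, given first high) | Share lost |
|---|---|---|---|
| 0.7 | 0.0083 | 0.331 | 67% |
| 0.8 | 0.0110 | 0.439 | 56% |
| 0.9 | 0.0148 | 0.593 | 41% |

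If only a share q of flagged values is rechecked within the visit, multiply by q. For q from 25% to 100%, the loss at r = 0.9 is 10% to 41%; at r = 0.7 it is 17% to 67%.

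**Step 3. Effect on a treatment difference.** Let LAT8881 raise the mean of both measurements by d SD. With S(x) = P(first > x) and B(x) = P(both > x),

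shrinkage = 1 − [B(1.96 − d) − B(1.96)] / [S(1.96 − d) − S(1.96)].

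| r | d = 0.25 | d = 1 |
|---|---|---|
| 0.7 | 55.7% | 42.6% |
| 0.8 | 45.7% | 34.5% |
| 0.9 | 32.5% | 24.2% |

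Worked case, r = 0.8 and d = 1: the true difference is 0.1685 − 0.0250 = 0.1435. Under the latest-value rule it is 0.1050 − 0.0110 = 0.0940. The shrinkage is 1 − 0.0940/0.1435 = 34.5%. With the planned 44 completers, the difference for one parameter falls from 44 × 0.1435 = 6.3 subjects to 44 × 0.0940 = 4.1. These figures also scale with q.

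**Step 4. Size of the row 4 loss.** This cannot be computed: the documents do not say how often unscheduled samples are expected.

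**The case against.** The strongest reply is that the exposure is narrow.

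- **Same-day blood repeats are probably uncommon.** Blood goes to a nominated laboratory, and safety results on Days 1 and 50 are not needed before dosing, so results are not expected during the visit. If the recheck is then an unscheduled visit, the scheduled abnormal value stays in the tables. The one test done on site, dipstick urinalysis, has no shift table, although SAP 11.7.2.1 does tabulate it by visit. This stands, subject to the unresolved meaning of visit/date.
- **The adverse event route catches what matters most.** A sample drawn between visits for a suspected problem is a likely candidate for Protocol 12.3, and adverse events are tabulated by treatment. This stands for clinically significant and symptomatic findings, but not for the rest.
- **Subjects who withdraw are asked for an end-of-study sample**, and SAP 11.7 summarises it under the last treatment taken. It is drawn about two weeks after the last dose, so it does not replace an on-treatment value.
- **Sometimes the repeat is the right value.** After a technical failure it is. This stands, and the fix keeps it.
- **Safety is descriptive, in about 55 subjects.** Listings can be read subject by subject. That lowers the stakes, but listings give no rate by treatment.

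A reader might infer that any abnormal value prompting a recheck disappears from the safety tables. The documents do not support that: the two rules act in opposite directions for a recheck, and the listings and adverse event tables remain. A reader might also infer that the rules favour LAT8881. They are prespecified and identical for both treatments.

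**Conclusion.** The point holds in a limited form. Followed as written, SAP 10.10 can displace a valid abnormal value when its repeat is recorded under the same visit/date, and SAP Section 8 leaves abnormalities first found between visits out of every laboratory table. The consequence is under-reporting in both treatment columns and a diluted difference, mainly for values judged not clinically significant.

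The 67%, 56% and 41% losses are upper bounds. They rest on complete rechecking within the visit, stable true values and assumed correlations; the real loss may be far smaller. Nor does a treatment difference shrink by those same percentages: for shifts of 0.25 to 1 SD the range is about 24% to 56% under the same full-recheck assumption. Because true values are held stable, the model describes measurement variation and does not size the loss of a transient drug effect.

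The choice between first and latest value at a visit is partly convention. The firmer gap is that no worst post-dose summary exists.

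**What to change.** 1. In SAP 11.7.2.2, add for each treatment period a shift from baseline to the worst post-dose category, including repeat and unscheduled results, as a stated exception to the Section 8 rule. Exclude only results documented as technically invalid. State the window, including how samples taken between the last dose of period 1 and the first dose of period 2 are assigned.
2. In SAP 10.10, let a repeat replace the original only when the original is documented as technically invalid; otherwise analyse the original in the by-visit tables.
3. In the same section, say whether a repeat on a later day belongs to the scheduled visit or is unscheduled.

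The cost is SAP wording and one derived record per parameter and period, with no new data collection. The downside is slightly higher and noisier abnormality rates in the worst-value table, which is why it should sit beside the by-visit tables and not replace them.

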10.12 Baseline

10.12.1 Safety Endpoints

For safety endpoints, latest measurement taken prior to Day 1 dosing in the first study period will be considered as baseline for both study periods.

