5.1 Overall study design

This is a randomised, placebo-controlled, double-blind, crossover, multi-site, Phase IIa study to investigate the efficacy and safety of oral LAT8881 in neuropathic pain. The overall study design is shown in Figure 4. Details of the procedures during each phase are described in Section 8.

The pharmacokinetics (PK) of LAT8881 will be investigated on Days 1, 28, 50 and 77 in 15 subjects (PK subjects) at Australian sites. Quantitative sensory testing (QST) will be performed in up to 20 subjects (QST subjects) before the first dose on Days 1 and 50 and after the morning dose on Days 28 and 77. PK subjects will not participate in QST measurements and QST subjects will not participate in PK analyses.

[figure not shown]

Figure 4: Overall study design for LAT-NP-001

Potential subjects will be required to provide written informed consent prior to any study-specific screening procedures being performed. Screening assessments will be performed from Day -28 to Day -1. Subjects deemed likely to be eligible for the trial will be given access to a diary during Screening Stage 1 and training on how to complete it from Days -7 to -1 inclusive (Screening Stage 2, first baseline period). These diary results will be reviewed on Day 1 to confirm that the subject is eligible for the study.

On Day 1, after the first baseline period, eligible subjects will be enrolled and randomised to LAT8881 or placebo. They will receive the investigational medicinal product (IMP) twice daily for four weeks (Days 1 to 28). On the morning of Day 28 they will return to the clinic for their end of first treatment visit and will take an IMP capsule in the morning during their clinic visit. They will take their final IMP dose for this treatment period in the evening.

The first treatment period will be followed by a washout period of two weeks (Days 29 to 42 inclusive) and then a second baseline period of one week (Days 43 to 49 inclusive). Over these days (i.e. Days 29-49 inclusive) subjects will not take any IMP.

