8.5 Second baseline period (Days 43-49)

During the second baseline period (Days 43 to 49 inclusive), subjects will continue their diary entries and will not take any IMP. They will record their NPRS rating each evening.

8.6 Second treatment period (Days 50-77), Visits 5 to 7

Subjects will return to the unit on Day 50 (± 1) with their diary completed from Days 29 to 49 inclusive and with their medication bottle.

8.6.1 Day 50 (± 1), Visit 5

Subjects will return on Day 50, and the following assessments will be undertaken:

- Review of the subject's pain diary (Days 43-49 inclusive)
- Weight
- ECG
- Vital signs
- Targeted physical examination, including assessment of area of pain
- · Concomitant medications
- Blood and urine samples for safety analysis (haematology, clinical chemistry, urinalysis)

Results from safety monitoring tests are not required prior to dosing. Subjects will also complete their second baseline assessments for Patient Reported Outcomes:

- Interference scale of short form BPI
- SF-MPQ-2
- NPSI
- BDI-II

In PK subjects, a pre-dose NPRS will be completed (maximum one hour before dosing) and a pre-dose blood sample taken for PK analysis. QST subjects will have a pre-dose QST assessment, if not completed within the previous 7 days.

Subjects (except for PK subjects) will take their allocated IMP and will remain in the clinic for up to one

hour to check for adverse events. Vital signs will be measured 30 (+/-10) minutes after IMP dosing.

PK subjects will take their allocated IMP and will remain in the clinic for at least 6 hours. At scheduled times (2, 5, 15, 30, 60 minutes, 2, 4 and 6 hours after IMP dosing), blood samples will be taken for PK analysis. NPRS will be monitored at 0.5, 1, 2, 4 and 6 hours. Vital signs will be measured 30 (+/-10) minutes after IMP dosing.

All subjects will leave the unit with sufficient IMP for the second treatment period. They will be reminded to complete their NPRS diary each evening.

8.6.2 Day 63 (± 1), Visit 6

On Day 63 (Visit 6), subjects will take their morning IMP dose and return to the clinic with their medication bottle. The following assessments will be undertaken:

- Weight
- Vital signs
- Targeted physical examination
- Concomitant medications
- Adverse events
- Compliance with medication
- Compliance with diary entries

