5.2 Second Baseline Period, Second Treatment Period and Follow Up

Visit No	Second Baseline Period	Second Treatment Period			End of Study
		5	6	7	
Study Day	43 to 49	50 ± 1	63 ± 1	77 ± 1	91 ± 2
Weight		X	X	X	X
12 lead ECG		X ¹⁹		X ¹⁹	
Vital signs		X ²⁰	X	X	X
Physical examination ²¹		X ²²	X ²²	X ²²	X ²²
Concomitant medications		X	X	X	X
Clinical laboratory safety testing ²³		X ^{19,24}		X ¹⁹	X
IMP administration		X ²⁷	X	X ²⁷	
Adverse event assessment		X	X	X	X
Blood sampling for PK analysis ²⁸		X ²⁹		X ²⁹	
Daily NPRS ratings ³⁰	X	X ³¹	X	X ³¹	
Short form BPI assessment		X		X	
Short form McGill questionnaire 2		X		X	
Neuropathic Pain Symptom Inventory		X		X	
Beck Depression Index-II		X		X	
PGIC				X	

19 Pre-dose

20 Pre-dose and 0.5 hours post-dose

21 Includes assessment of area of pain

22 Targeted physical examination

23 Haematology, biochemistry, urinalysis

24 Results of clinical laboratory tests not required prior to dosing

27 Supervised administration

28 PK subjects only

29 Pre-dose and up to 8 hours post-dose

30 Each evening throughout baseline and treatment periods

31 Additional ratings pre-dose and up to 8 hours post-dose in PK subjects

6 Interim Analysis

There is no interim analysis planned for this study.

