10.13 Change from Baseline

Change and % Change between Baseline and post-baseline result will be calculated for all efficacy and safety endpoints within each study period as below:

- Change = Result at Day x – Baseline Result
- % Change = _____x100

When baseline NPRS score = 0, % change from baseline will be calculated using an imputed value of 0.1 at baseline. The range of the NPRS score is 0-10; an imputed value of 0.1 is deemed small enough to be close to zero for percentage change calculations. This imputation will not be included in absolute or change from baseline results.

For subjects with NPRS collected at timepoints in baseline and week 4 visits, change and % change from baseline will be calculated using pre-dose values for timepoints 0.5, 1, 2, 4, 6 hours at each visit.

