11.7 Safety Analyses

All safety summaries will be based on the Safety population. Screening visits will not be included in summaries, and will only be listed. Baseline measurements will be summarized under 'PreTreatment' for all safety summaries. EOS / Early Termination visits will be summarized in 'Total' within last treatment taken.

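### The safety baseline is fixed at Day 1 for both periods, so Period 2 laboratory and vital-sign changes and blood-test shifts include anything already present before the Day 50 dose

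*SAP*

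**What the plan says.** SAP 10.12.1 sets one safety baseline: the "latest measurement taken prior to Day 1 dosing in the first study period will be considered as baseline for both study periods". SAP 10.13 adds that change and percentage change "will be calculated for all efficacy and safety endpoints within each study period". SAP 11.7 gives the baseline one place in the tables: "Baseline measurements will be summarized under 'PreTreatment' for all safety summaries".

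A second pre-dose set of values is collected. The schedules in Protocol 2.2 and SAP 5.2 mark the Visit 5 (Day 50) laboratory tests and ECG as pre-dose, and the vital-signs footnote for that visit reads "20 Pre-dose and 0.5 hours post-dose". Protocol 8.6.1 confirms the later reading: "Vital signs will be measured 30 (+/-10) minutes after IMP dosing". Day 50 follows an off-drug interval (Protocol 5.1): "Over these days (i.e. Days 29-49 inclusive) subjects will not take any IMP".

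SAP 10.4 places Days 43 to 91 in study period 2. SAP 10.3 gives Day 1 and Day 50 the same analysis visit, Visit 2/Visit 5, and Days 28 and 77 the same visit, Visit 4/Visit 7. Laboratory changes (SAP 11.7.2.1) and vital-sign, weight and BMI changes (SAP 11.7.3.2) are reported by treatment, overall and within each period. Shift tables for haematology, clinical chemistry, liver function and coagulation follow the same pattern (SAP 11.7.2.2).

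Efficacy is handled differently: SAP 10.12.2 uses a Period 2 baseline taken before the Day 50 dose. SAP 12 gives no reason for the difference, and the protocol defines no safety baseline for Period 2.

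**The concern.** A by-treatment table of change or shift is read as what happened on that treatment. With the Day 1 baseline, the Period 2 entries also contain what happened during Period 1 and the three off-drug weeks. The Day 50 pre-dose sample is the clearest case. Under SAP 10.3, 10.4 and 10.12.1 it is a post-baseline Period 2 result, although the subject has not yet taken the Period 2 treatment.

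Two consequences matter for reading the safety tables. First, a blood-test abnormality that arises in Period 1 and persists is tabulated as a shift under both treatments, which blurs its origin. Second, the 0.5-hour vital-sign reading, whose purpose is to show an acute effect, is compared with a same-visit value on Day 1 but with a value seven weeks old on Day 50. The overall-by-treatment summary of Visit 2/Visit 5 then pools two different quantities.

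**Working it through.** The documents give no figure for a safety change, so there is none to reproduce. The sample size of 44 concerns the NPRS and is not involved.

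**1. Time spans (study days from the schedules)**
- Day 1 to Day 50: 50 - 1 = 49 days, or 7 weeks (48 to 50 with the 1-day visit window). Of these, 28 are on Period 1 treatment (Days 1-28) and 21 are off drug (Days 29-49).
- Day 1 to Day 28: 27 days. Day 50 to Day 77: 27 days. Day 1 to Day 77: 76 days.
- Share of the Day 77 change that precedes any Period 2 dose: 49/76 = 64% of the span.

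For a result Y, (Y77 - Y1) = (Y50 - Y1) + (Y77 - Y50). Only the second term belongs to Period 2 treatment time.

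**2. A persistent abnormality in the shift tables**

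Take a subject in the LAT8881-placebo sequence who is normal before Day 1 dosing and abnormal at Days 28, 50 (pre-dose) and 77.

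| Visit | Treatment column | Day 1 baseline | Period baseline |
|---|---|---|---|
| Day 28 | LAT8881 | normal to abnormal | normal to abnormal |
| Day 50 pre-dose | placebo | normal to abnormal | is the baseline |
| Day 77 | placebo | normal to abnormal | abnormal to abnormal |

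The reverse sequence mirrors this: an abnormality that arises on placebo and persists is counted under LAT8881.

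**3. Precision of the 0.5-hour change on Day 50**

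With equal variances (assumption), SD of change = SD x sqrt(2(1 - r)). The correlations are assumptions; the documents give none.
- Same-visit baseline: r = 0.9 gives 0.447; r = 0.8 gives 0.632.
- Day 1 baseline: r = 0.7 gives 0.775; r = 0.6 gives 0.894.
- Ratios: 0.775/0.447 = 1.73 and 0.894/0.447 = 2.00 for within-visit r = 0.9; 0.775/0.632 = 1.22 and 0.894/0.632 = 1.41 for within-visit r = 0.8.

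**4. Effect on the LAT8881-placebo difference**

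Let t be the true effect at the end of a period, g a linear drift per day, and r50 and r77 the LAT8881 effect left over from Period 1 at Days 50 and 77. Assume balanced sequences and equal completion.
- Day 1 baseline: the LAT8881 mean is t + (27g + 76g)/2 and the placebo mean is r77/2 + (27g + 76g)/2. The difference is t - r77/2.
- Day 50 baseline in Period 2: the LAT8881 mean is t + 27g and the placebo mean is (r77 - r50)/2 + 27g. The difference is t - (r77 - r50)/2.

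Drift drops out of both differences but changes the displayed level. With g = 0.02 and no drug effect (assumed), the Day 77 change is 76 x 0.02 = 1.52 from Day 1, against 27 x 0.02 = 0.54 from Day 50, in both treatments.

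Assumed residuals with t = 1:

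| r50 | r77 | Day 1 baseline | Day 50 baseline |
|---|---|---|---|
| 0.5 | 0.5 | 0.75 | 1.00 |
| 0.5 | 0.25 | 0.875 | 1.125 |
| 0.5 | 0 | 1.00 | 1.25 |

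**The case against.** The case for leaving the rule alone is a fair one. Day 1 is the only treatment-naive reference for both sequences. The last row of the second table shows that if a residual effect fades during Period 2, the Day 1 baseline returns the true contrast and the Day 50 baseline does not. A Day 50 baseline also removes a lasting LAT8881 abnormality from the Period 2 shifts. This stands, and it rules out simply replacing Day 1.

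Much of the information can also be recovered. Absolute results appear by period, visit and, for vital signs, timepoint. The mean acute change on Day 50 can therefore be obtained by subtraction if pairs are complete, though its SD cannot. Shifts are shown by visit, so one already present at Day 50 pre-dose can be recognised by a reader who knows that the sample precedes dosing. Individual laboratory results are listed.

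Clinically significant findings must also be recorded as adverse events (Protocol 12.3). SAP 10.9 allocates an event that starts in Period 1 or washout to the Period 1 treatment and marks it Ongoing in Period 2. The overall adverse-event table by treatment counts only New events (SAP 11.7.1.1). This covers the most important cases, but not abnormalities judged not clinically significant, and the overall-by-treatment tables by system organ class and preferred term include Ongoing events as well (SAP 11.7.1.2).

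Finally, the table shells are in the Data Display Plan, which is not among the documents. How the Day 50 pre-dose row will be labelled cannot be confirmed.

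**Conclusion.** The point holds as a minor one. It is confined to the laboratory and vital-sign (with weight and BMI) change tables and the blood-test shift tables. There, Period 2 entries include pre-existing change, persistent Period 1 abnormalities appear under both treatments, and the pooled Visit 2/Visit 5 vital-sign change mixes a within-visit with a 49-day difference. The SD ratio of 1.2 to 2.0 applies only to the Day 50 0.5-hour change and depends wholly on the assumed correlations.

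A reader might infer more than the documents support:
- That Period 1 drug effects in general are credited to the Period 2 treatment. Only effects that outlast 21 off-drug days can be.
- That seven weeks of drift bias the treatment comparison. Drift moves the change shown under each treatment but largely cancels in the contrast, provided sequences and completion are balanced. The available text does not state the allocation ratio.
- That ECG results are distorted. SAP 11.7.3.4 tabulates ECG findings by visit, with no change or shift from baseline.
- That a test or error rate is affected. SAP 8 makes safety descriptive.
- That all Period 2 changes are noisier by the same factor. No correlations are available for the Day 77 comparison.

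**What to change.** In SAP 10.12.1, for laboratory and vital-sign changes and blood-test shifts by treatment, add a period-specific baseline: the last value before the first dose of each period. Label the Day 50 pre-dose value as the Period 2 baseline, not as a result under the Period 2 treatment, and carry that label into SAP 10.3, SAP 11.7 and the table shells. Calculate the 0.5-hour vital-sign change on Days 1 and 50 from the pre-dose value at the same visit. Keep change and shift from Day 1 alongside as the treatment-naive reference.

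No new data are needed. The cost is SAP wording, one more derived baseline and extra table columns. A residual Period 1 effect must then be read from the Day 1 columns, and a table note should say that a residual effect fading during Period 2 can bias the change measured from Day 50.
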